9.4 STATISTICAL ANALYSES

This is a pilot study collecting data for OCT and a/LCI-OCT device optimization. This study will provide initial images for the investigational device, and depending on the device's accuracy in discerning tissue, these data will help form the basis for further investigations. Data analysis will consist of simple bivariate analysis, with endoscopy results being compared to a/LCI-OCT image results. Specifically, 2 x 2 tables of OCT, a/LCI-OCT, and endoscopy results will be constructed, with each imaging site being categorized as columnar versus squamous. Sensitivity will be defined as the proportion of sites correctly categorized by OCT, or a/LCI-OCT, using endoscopy results as the gold standard. Measures of variability of sensitivity results will be generated using non-parametric statistics.

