1 PROTOCOL SUMMARY

1.1 SYNOPSIS

Title: Advanced a/LCI Systems for Improved Clinical Utility: An Optical Coherence Tomography (OCT) Pilot Study (OCT Pilot)

Study Description: This is a pilot study to test the operating characteristics of a newly developed dual modality probe including optical coherence tomography (OCT) and angle-resolved low-coherence interferometry (a/LCI) in human subjects, and to collect data for further optimization of the a/LCI-OCT device. Phase I will incorporate the single modality OCT probe. Phase II will consist of a dual modality probe to include both OCT and a/LCI components.

Potential subjects will be presenting to a UNC Endoscopy unit for routine upper endoscopy (EGD) for clinical signs or symptoms. If eligible, informed consent will be obtained prior to undergoing this routine care upper endoscopy. During the endoscopy, and prior to taking any biopsies, the probe will be attached to the end of the endoscope and passed with the endoscope into the esophagus. The probe will make contact with the epithelium of the esophagus, and data will be collected as part of this research study to identify operating characteristics of the new OCT device and the a/LCI-OCT combined device. Esophageal images and pictures will be obtained during the procedure and will be used in this study. If biopsies are taken for routine care (clinical biopsies), then results from those biopsies will be used in this study. For a subset of subjects, participating in the combined-modality probe, study-specific biopsies will be taken at the same location the probe is deployed, to allow comparison of data from the imaging modalities to “gold-standard” biopsy data. Additionally, slides may be requested from clinical biopsies for use in this study after they have yielded their results for routine care.

Objectives: To test a newly developed imaging device in human subjects to determine 1) whether adequate tissue contact can be attained to acquire high quality images, and 2) to identify if these images can discern whether the imaged tissue is squamous or Barrett's Esophagus (BE) epithelium.

Endpoints: None

Study Population: Patients of UNC Healthcare undergoing routine care endoscopy with or without Barrett's Esophagus. Target enrollment includes two cohorts, with an approximate enrollment of up to 82 subjects. Cohort A will consist of 14 subjects in each of 3 groups; normal asymptomatic controls, non-dysplastic Barrett's Esophagus, and

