5 STUDY POPULATION

5.1 INCLUSION CRITERIA

Subjects must meet all of the following criteria to be eligible for this study:

1. Presenting to UNC for routine care upper endoscopy
2. Meet one of the following criteria:
 - 2.1. Cohort A
 - 2.1.1. Presenting to UNC for upper endoscopy of GI conditions without esophageal symptomatology with no history of gastroesophageal reflux disease (GERD) or other esophageal condition affecting the epithelium (asymptomatic controls). Esophageal

symptomology includes, but is not limited to, heartburn, globus, chest pain, dysphagia, and odonophagia OR,

- 2.1.2. Current dysplastic or non-dysplastic Barrett's Esophagus of any length OR,
- 2.1.3. History of dysplastic or non-dysplastic Barrett's Esophagus after treatment with endoscopic eradication therapy (EET)

OR

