8.1.2.1 PROBE ADMINISTRATION, ESOPHAGEAL IMAGES, AND RESEARCH BIOPSIES

Subjects will proceed with routine care EGD, during which esophageal landmarks will be identified, and the OCT or a/LCI-OCT device administered. In brief, the probe will be affixed to the end of the endoscopy using a plastic band, in a manner similar to that used to deliver other devices into the esophagus. The device and endoscope tip will be passed through the posterior pharynx and the upper esophageal sphincter under direct endoscopic visualization. Areas of normal squamous epithelium can be easily identified endoscopically, as can areas of columnar mucosa in the esophagus, based on the endoscopic appearance. The OCT or a/LCI-OCT combined device will be apposed to both normal and columnar (Barrett's) tissue, by deflection of the endoscope tip. Images will be acquired by the device, as detailed below, and subjects enrolled in cohort B will also receive research-specific biopsies as detailed below. The indentation on the tip of the probe will create a transient tissue bump that is visible endoscopically to allow for concurrent research biopsies after images are taken. After acquisition of these images and research biopsies (as applicable), the remainder of the study will be performed as per the standard of care.

Erosions, erosive disease, and areas of inflammation will be avoided when placing the paddle for probe administration. Adequacy of device-to-epithelium contact will be measured based on the quality of the OCT image. In images with poor contact, esophageal mucosal layers are poorly defined. In this situation, the probe will be repositioned in an effort to improve image quality. A good image is that in which esophageal mucosal layers are clearly defined in the OCT image.

COHORT A:

During the procedure, the OCT device will be administered, and at least one white light image and at least one narrow band image will be taken from the following locations of the esophagus:

- 1) 3 centimeters above the top of the gastric folds (TGF-3)
- 2) 5 centimeters above the top of the gastric folds (TGF-5)
- 3) Any planned clinical biopsy locations

COHORT B:

During the procedure, the a/LCI-OCT device will be administered, and at least one white light image and at least one narrow band image will be taken from the following locations of the esophagus:

- 1) 3 centimeters above the top of the gastric folds (TGF-3)
- 2) 5 centimeters above the top of the gastric folds (TGF-5)

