9.2 SAMPLE SIZE DETERMINATION

Cohort A will be imaged with OCT. Previous data on OCT demonstrate that established systems are sensitive with respect to detecting Barrett's mucosa. For instance, Poneros et al (2001) found a 97% sensitivity rate using OCT in 38 patients²⁹. At this stage of development, if we can achieve at least 70% sensitivity, then the device will pass initial testing. If optimal sensitivity is 95%, and the lowest acceptable sensitivity is 70%, then we will require at least 14 patients with evaluable data in each group (42 total in Cohort A) to assess whether the device adequately meets this threshold with 85% power.

Cohort B will be imaged with a/LCI. Our group previously conducted and published a study in 2011 using single-point a/LCI to measure nuclear diameter as an indicator of dysplasia in the esophagus.¹³ The primary differentiating characteristic between dysplastic and normal tissue was nuclear diameter (measured by a/LCI). For dysplastic tissue, the mean nuclear diameter and standard deviation was $13.0 \pm 1.1 \mu\text{m}$, and for normal tissue, the same respective values were $10.3 \pm 1.7 \mu\text{m}$. This difference was highly statistically significant, and we rejected the null hypothesis (no difference between normal and dysplastic nuclear diameters) with a p-value of 0.0001.

To determine the number of targeted patient enrollments in Cohort B, we conducted a statistical power analysis based on our previous results. For a sample size of 20 patients with dysplasia and 20 patients with normal esophageal tissue, and targeting the same p-value of 0.0001, we expect a robust statistical power of 97% when conducting a two-sample t-test for nuclear diameter distributions matching our observations from the 2011 study. We would therefore expect a 97% chance of validating our previous observations at the same level of significance for a sample size of 20. Comparatively, for a sample size

of 10 patients in each category, our power would be only 36%, far too low; for a sample size of 30 patients in each category, our power would be greater than 99.9%, which is unnecessarily high. Therefore, for Cohort B, we will target 20 patients with dysplasia and 20 normal patients to achieve a strong statistical power without an undue excess in patient enrollment.

To accommodate Cohort B, which will be receiving the dual modality a/LCI-OCT probe, we have therefore changed the sample size to be a total of 82 (42 in Cohort A, and 40 in Cohort B).

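### Section 9.4 defines sensitivity as the share of all sites correctly classified, which is overall accuracy, so the 70% pass mark no longer measures Barrett's detection

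*Combined protocol and SAP*

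**What the plan says.** Section 9.4 plans 2 x 2 tables of device result against endoscopy, "with each imaging site being categorized as columnar versus squamous". The next sentence reads: "Sensitivity will be defined as the proportion of sites correctly categorized by OCT, or a/LCI-OCT, using endoscopy results as the gold standard". It names no denominator other than sites, and it does not define specificity.

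Section 9.2 uses the word in its ordinary sense. It introduces the Cohort A sample size with "Previous data on OCT demonstrate that established systems are sensitive with respect to detecting Barrett's mucosa" and then sets the pass mark: "At this stage of development, if we can achieve at least 70% sensitivity, then the device will pass initial testing". It takes 95% as optimal and 70% as lowest acceptable, and asks for 14 evaluable patients per group "to assess whether the device adequately meets this threshold with 85% power".

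Section 9.1 plans no hypothesis tests and lists sensitivity and specificity as separate estimates, each with a 95% confidence interval.

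Squamous tissue will be in the tables. The Synopsis says "Cohort A will consist of 14 subjects in each of 3 groups; normal asymptomatic controls, non-dysplastic Barrett's Esophagus", the third group being current or past dysplastic Barrett's. Section 8.1.2.1 says "The OCT or a/LCI-OCT combined device will be apposed to both normal and columnar (Barrett's) tissue, by deflection of the endoscope tip". It also treats the unbiopsied epithelium of subjects without esophageal symptoms as squamous, and lets the number and location of images vary without a deviation. Section 5.1 admits patients whose Barrett's has been treated by eradication therapy and who may have no columnar site left.

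**The concern.** A squamous site called squamous is correctly categorised, so under the Section 9.4 wording it counts towards sensitivity. The result is overall accuracy, which mixes Barrett's detection with correct recognition of normal tissue in proportions set by how many sites of each kind are imaged.

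The 70% figure is the plan's only pass rule, and Section 9.4 is the only place where the quantity it applies to is defined. Followed literally, the number reported as sensitivity and set against 70% is not the Barrett's detection rate, and it moves with a site mix that is not fixed in advance. A device that misses many Barrett's sites could pass because it recognises squamous tissue well. One that finds nearly all of them could fall short because it over-calls squamous tissue. Section 9.4 makes further work depend on how accurately the device discerns tissue, and Section 10.1.2 allows interim looks at device performance that could end the study. A mislabelled figure could enter both decisions.

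**Working it through.** **Inputs.** From Section 9.2: p0 = 0.70, p1 = 0.95, n = 14 per group, power 85%. From the Synopsis: 14 of 42 Cohort A subjects are controls. Not in the documents, so assumed over a range: specificity Sp, and the squamous share of sites s. Se is true sensitivity for columnar sites.

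**Step 1: the plan's own figure.** Sections 9.1 and 9.2 give no alpha and no decision rule, so the rule has to be inferred from the stated power. For X ~ Binomial(14, p):

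| Rule | P(pass) at p = 0.95 | P(pass) at p = 0.70 |
|---|---|---|
| at least 12 of 14 | 97.0% | 16.1% |
| at least 13 of 14 | 84.7% | 4.75% |
| 14 of 14 | 48.8% | 0.7% |

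Of these cut-offs only 13 of 14 matches 85%. The plan's figure therefore reproduces as a one-sided exact binomial rule at about 5%, with 14 independent units.

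**Step 2: what Section 9.4 measures.**

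A = (1 − s) × Se + s × Sp

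Setting A = 0.70 and solving gives Se = (0.70 − s × Sp) / (1 − s). For example, with s = 1/2 and Sp = 0.95: (0.70 − 0.475) / 0.5 = 0.45.

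True sensitivity at which the Section 9.4 measure equals 70%:

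| Sp | s = 1/3 | s = 1/2 | s = 2/3 |
|---|---|---|---|
| 0.60 | 75% | 80% | 90% |
| 0.70 | 70% | 70% | 70% |
| 0.80 | 65% | 60% | 50% |
| 0.95 | 57.5% | 45% | 20% |
| 1.00 | 55% | 40% | 10% |

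The direction holds for any mix containing both tissue types; only the size depends on s. This table needs no decision rule.

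**Step 3: a count illustration.** Assume one site per Cohort A patient, 28 columnar and 14 squamous. If all 14 squamous sites are right, 30 correct of 42 (71%) meets the mark with 30 − 14 = 16 of 28 Barrett's sites detected, which is 57%.

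**Step 4: pass probabilities under the inferred 13-of-14 rule**, taking P(X ≥ 13) with p = A:

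| Se | Sp | s = 1/3 | s = 1/2 | s = 2/3 | Usual definition |
|---|---|---|---|---|---|
| 0.70 | 0.60 | 2.7% | 2.1% | 1.5% | 4.75% |
| 0.70 | 0.80 | 8% | 10% | 13% | 4.75% |
| 0.70 | 0.95 | 16% | 27% | 43% | 4.75% |
| 0.95 | 0.80 | 58% | 46% | 36% | 85% |
| 0.50 | 0.95 | 2% | 7% | 20% | 0.1% |

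Fixing the columnar/squamous counts at 9/5, 7/7 and 5/9 instead of drawing them at random changes the third row to 16%, 25% and 38%.

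**Step 5: sensitivity to the rule.** Section 9.2 can also be read as observed sensitivity of at least 70%, which is 10 of 14. The Se 0.50, Sp 0.95 device then passes 42%, 67% and 87% of the time, against 9% under the usual definition.

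**The case against.** The strongest reply is that the wording is loose rather than wrong. The definition follows directly on a 2 x 2 table, the term has a standard meaning, Section 9.1 lists specificity separately and Section 9.2 speaks of Barrett's mucosa, so an analyst would probably compute the conventional figure. The second study objective is also to tell squamous from Barrett's tissue, which correct classification over both types does address. The usual meaning probably was intended. But no section states a columnar-only denominator, and the one sentence that defines the estimate gives a different quantity.

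The pass probabilities are open to more criticism. The 13-of-14 rule is inferred, and 13 of 14 is 93% observed, well above the 70% written. Under the 10-of-14 reading a device with true sensitivity of 70% passes 58% of the time under the usual definition, so calling that device one that should fail depends on the inferred rule. Fourteen is also a count of patients, whereas Section 9.4 counts sites. Pooling 42 units with a cut-off of 35 (3.8% at 70%) moves the Se 0.70, Sp 0.95 row to 28%, 54% and 81%. These points stand as limits on the Step 4 and Step 5 sizes. They do not affect the break-even table or the direction.

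It is also fair that little is lost: no endpoints, no hypothesis tests, images that do not guide care, and all four cells retained.

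**Conclusion.** The concern holds. As written, Section 9.4 calls overall accuracy sensitivity, and reaching 70% on it does not show 70% Barrett's detection. The gap closes only when specificity equals 70% at the threshold. Over the assumed ranges (specificity 60% to 100%, squamous share 1/3 to 2/3), the sensitivity that meets the mark runs from 10% to 90%. That result rests on algebra plus the assumed specificity and site mix. The pass probabilities rest further on an inferred rule and independent units, and should be read as illustrations.

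This should be fixed, but its reach is modest. It is a wording error that yields a wrong headline figure in a pilot where passing means further development. It loses no data and does not by itself call for a different sample size.

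**What to change.** In Section 9.4, replace the definition with two:

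- Sensitivity: columnar sites called columnar by the device, divided by all endoscopically columnar sites.
- Specificity: squamous sites called squamous by the device, divided by all endoscopically squamous sites.

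Report overall accuracy under that name, with the counts of columnar and squamous sites. State that the 70% mark in Section 9.2 applies to sensitivity so defined, and report specificity with its 95% confidence interval beside it, so that a device calling every site columnar is not read as a success.

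The cost is a sentence or two, with no new data, since the four cells are already planned. The price is a smaller denominator and wider intervals. With illustrative counts treated as independent, the exact 95% interval is 67% to 96% for 24 of 28 columnar sites, against 75% to 91% for 71 of 84 sites of both kinds. Controls, and treated patients with no columnar tissue left, would contribute to specificity only.

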The Seattle biopsy protocol is used for standard of care (SOC) which includes taking 4 quadrant biopsies every one to two centimeters throughout the area of interest. Because we generally take these biopsies every two centimeters, up to 10 research biopsies in addition to SOC biopsies would generally be within the total number of biopsies advocated as the standard of care (give our mean BE segment length of 4-5 cm). It should also be noted that no higher incidence of complications has been documented by taking biopsies by the more aggressive biopsy protocol (4 biopsies every one cm) than the less aggressive (4 biopsies every two cm) protocol.

Given the excellent safety profile of these imaging techniques, the risks and costs inherent in the current standard of care, the potential benefits of this investigation outweigh the risks.

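### Section 9.4 pools imaging sites to estimate sensitivity while section 9.2 sizes the 70% mark on patients; a patient-averaged sensitivity should be reported beside the pooled value and read against 70%

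*Combined protocol and SAP*

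**What the plan says.** **Estimation.** Section 9.4 builds 2 x 2 tables "with each imaging site being categorized as columnar versus squamous", with endoscopy as the reference, and then states: "Sensitivity will be defined as the proportion of sites correctly categorized by OCT, or a/LCI-OCT". It gives no per-patient summary, weight or cap, and does not restrict the denominator to columnar sites. On precision it says only: "Measures of variability of sensitivity results will be generated using non-parametric statistics". Section 9.1 rules out hypothesis tests and promises 95% confidence intervals.

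**Sizing.** Section 9.2 says of Cohort A that "if we can achieve at least 70% sensitivity, then the device will pass initial testing". Taking 95% as optimal and 70% as the lowest acceptable sensitivity, it concludes "we will require at least 14 patients with evaluable data in each group" for 85% power.

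**Number of sites.** Section 8.1.2.1 images at 3 cm and 5 cm above the gastric folds (TGF-3, TGF-5) and at "Any planned clinical biopsy locations". It also allows the number and location of images to vary without counting as a deviation. Section 2.3.3 describes standard-of-care sampling as "4 quadrant biopsies every one to two centimeters throughout the area of interest", generally every 2 cm at this centre, with a mean segment length of 4-5 cm. Section 5.1 admits "Current dysplastic or non-dysplastic Barrett's Esophagus of any length".

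**The concern.** Read together, these sections let the number of columnar sites per patient grow with the extent of disease. A pooled proportion weights each patient by that number, whereas section 9.2 counts each patient once. If sensitivity is related to segment length, the two weightings give different answers.

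This is separate from the usual clustering problem. A patient-level bootstrap around the pooled proportion would give a more honest interval, but it would leave the point estimate unchanged.

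What is at stake is the figure read against 70%, and through it whether the device passes initial testing. Section 10.1.2 also provides for interim assessments of device performance that may lead to early termination. The plan should make clear whether such a figure reflects most patients or a few with many sites.

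**Working it through.** **1. Reproduce the plan's figure.** Inputs from section 9.2: n = 14, lowest acceptable 0.70, optimal 0.95. No alpha is stated for Cohort A; one-sided 0.05 is assumed. Treat each patient as one binary result and require at least 13 of 14 correct.

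- Power at 0.95: 14 × 0.95^13 × 0.05 + 0.95^14 = 0.359 + 0.488 = 0.847.
- Alpha at 0.70: 14 × 0.70^13 × 0.30 + 0.70^14 = 0.0407 + 0.0068 = 0.0475.

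So 14 patients and 85% power fit a calculation with one observation per patient.

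**2. Difference between the two estimates.** Let patient i have m_i columnar sites and sensitivity p_i.

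- Pooled = Σ m_i p_i / Σ m_i.
- Patient-averaged = mean of p_i.
- With only two levels of sensitivity, short and long segment: pooled − patient-averaged = (long-segment share of sites − long-segment share of patients) × (p_long − p_short).

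**3. Two equal groups.** Assume half the patients have 2 cm segments and half 8 cm, with four quadrants at each 2 cm level counting both ends, and leave out TGF-3 and TGF-5. That gives 8 and 20 sites. The multiplier is 20/28 − 1/2 = 0.214.

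- 10-point gradient: 0.214 × 10 = 2.1 points.
- 92% versus 98%, close to section 9.2's optimal value: 0.214 × 6 = 1.3 points.
- 50% versus 90%: patient average 70.0%, pooled (8 × 0.5 + 20 × 0.9)/28 = 78.6%.
- Reversed (90% versus 50%): 70.0% and 61.4%.
- No gradient: no difference.

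With 4 versus 20 sites (1 cm and 8 cm) the multiplier is 20/24 − 1/2 = 0.333, so a 10-point gradient moves the estimate 3.3 points.

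**4. Mean length near the documented 4-5 cm.** The individual lengths and the sensitivities are assumptions. Here sites are four per 2 cm level, with the number of levels equal to length/2 rounded up, plus TGF-3 and TGF-5 where the segment reaches them.

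| | Spread-out set | Narrow set |
|---|---|---|
| Lengths (cm) | 1,1,1,1,2,2,2,3,4,6,8,9,10,12 | 2,2,3,3,4,4,4,5,5,5,6,6,7,7 |
| Mean length | 4.4 | 4.5 |
| Columnar sites per patient | 4 to 26 | 4 to 18 |
| Total sites | 148 | 159 |
| Share of sites from the 4 longest segments | 88/148 = 59% | 40% |
| Share of patients above 3 cm | 6/14 = 0.429 | 10/14 = 0.714 |
| Share of sites from patients above 3 cm | 111/148 = 0.750 | 133/159 = 0.836 |
| Multiplier | 0.321 | 0.122 |
| Shift for a 10-point gradient | 3.2 points | 1.2 points |
| 60% / 80%: patient average, pooled | 68.6%, 75.0% | 74.3%, 76.7% |
| 80% / 60%: patient average, pooled | 71.4%, 65.0% | 65.7%, 63.3% |
| Effective number of equally weighted patients, (Σm)²/Σm² | 9.0 | 12.2 |

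In the spread-out set a 20-point gradient puts the two estimates on opposite sides of 70%. In the narrow set it does not.

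**The case against.** The strongest reply is that the pooled proportion is not wrong. Sections 1.1 and 3 ask whether images can tell if the imaged tissue is squamous or Barrett's, which is a tissue-level question. The synopsis lists no endpoints for this pilot. Section 9.2 counts patients but never says that sensitivity is averaged over them. This stands: the pooled value is a legitimate site-level estimate, and calling it biased presupposes a patient-level target.

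A reader might infer that long-segment patients do drive the estimate, and that a device failing the average patient would pass. The documents do not support that, for four reasons.

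- They give no sensitivity by segment length. The probe housing is about 23 mm long (section 6.1.1), which might suggest poorer contact in short segments, but no section links segment length to contact or image quality.
- A reversal such as 62.5% patient-averaged against 72.1% pooled needs 40% versus 85% sensitivity, a 45-point gradient, with nobody near the stated mean length.
- Site counts are inferred. The biopsy pattern comes from the risk discussion in section 2.3.3, and clinical biopsies are conditional in section 4.1. Without them a patient may supply only TGF-3 and TGF-5.
- A reversal also needs the pass mark to be a point estimate of at least 70%. Under the 13-of-14 rule (93%) that reproduces the stated power, neither 62.5% nor 72.1% passes. Precision is low in any case: an exact 95% interval for 10 of 14 patients runs from 42% to 92%.

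It is also fair to say that a mean of within-patient proportions is not identical to the single binary result per patient behind section 9.2, and that it is undefined for patients with no columnar sites. The first is a limit of the remedy; the second needs an explicit rule.

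What survives is that sizing and estimation use different units, with nothing in the plan to show whether this matters.

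**Conclusion.** The mismatch is real and its likely effect is modest. Section 9.4 estimates on the site scale, section 9.2 sizes on the patient scale, and site counts are uncapped and tend to rise with segment length. For a 10-point gradient the shift is 2.1 points with 8 versus 20 sites, and between 1.2 and 3.3 points across the configurations tried. It is larger only with large gradients or very uneven site counts, can go either way, and is zero without a gradient.

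This rests on assumed segment lengths, site counts and sensitivities; only the 4-5 cm mean, the biopsy pattern and the imaging locations come from the protocol. The documents do not show that the pooled result will mislead. They leave the reader unable to tell, which is cheap to put right before analysis and prevents the unit being chosen after the results are seen. It is a worthwhile improvement rather than a flaw that undermines the study.

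**What to change.** Amend section 9.4 as follows.

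1. Define sensitivity over columnar sites only and specificity over squamous sites only, by the endoscopic reference. Read literally, the present definition counts correct calls at all sites, which is overall accuracy.
2. Next to the pooled value, report the mean over patients of each patient's proportion of columnar sites correctly called, with a 95% interval from a bootstrap that resamples patients.
3. State that this patient-averaged value is the one read against the 70% mark.
4. State that patients with no columnar sites contribute to specificity only. This covers controls and may cover some patients treated with eradication therapy (section 5.1).
5. Show results by segment length.

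The cost is a few sentences and no additional procedures, assuming that segment length is among the endoscopy data collected under section 8.1.2, which does not itemise them. The statistical price is that patients with few sites contribute noisier proportions, so the patient-averaged estimate may be slightly less precise.
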